12.4. Risks to others who are not subjects: n/a

12.5. Procedures performed to lessen the probability or magnitude of risks:

To mitigate these risks, we will emphasize the voluntary nature of the study to adolescents and parents and that the study will in no way impact or influence clinical care. We will let adolescents know that their information will be kept confidential and that transcripts will be de-identified and audio recordings destroyed after transcribing. We will let patients know that their A1c data may be available to their providers. We will let adolescents know that they can change their mind about participating and may decide to withdraw from the study at any time.

Each of the participating sites has significant experience with clinic recruitment for studies and has developed processes to ensure best practices with each study participant recruitment. These procedures and scripts also emphasize that any potential coercion on the part of parents should not take place, and that adolescents' decision for or against participation in the study does not affect the clinical care they receive.

Protocol Version Number: 10
Protocol Version Date: 7/28/2021

The investigators and staff will be available to answer any questions from potential participants via phone or email throughout the study. We will emphasize that the decision of whether or not to be part of this study does not affect their ongoing care at their respective institutions.

13. Potential Benefits to Subjects

13.1. Potential benefits that individual subjects may experience from taking part in the research:³²

We hypothesize that patients who receive the intervention will have better clinical and psychosocial/behavioral outcomes. However, there may be no direct benefit for participating in this study if our hypotheses are wrong. More broadly, information gained from this study may heighten the understanding of the adolescent diabetes experience and elucidate strategies that foster resilience and promote better outcomes in this group of high risk patients. These strategies could be extended to the care of other adolescent patients facing other chronic diseases. This research has the potential to contribute to the research base concerning the promotion of optimal quality of life and mental wellness for all adolescent patients.

14. Data Analysis/Management

14.1. Data analysis plan, including statistical procedures:

Randomization. The randomization algorithm will be constructed by the study statisticians ([name] and [name]) using a permuted blocks scheme with varying block sizes; randomization will be stratified by site. Study staff will be blinded to allocation until after enrollment.

Analysis plan overview. The primary statistical analyses will be intention-to-treat to avoid confounding by non-random participant attrition. Clinical characteristics including A1C and time in range and items within the surveys will all be summarized at time of enrollment and at 3, 6, 9 and 12-month time points using descriptive statistics: frequencies and proportions for categorical variables, means and standard deviations for continuous variables, or median and inter-quartile range if distribution is skewed. Demographic characteristics will be collected and summarized at baseline. All analyses will be adjusted for site and baseline A1C, as randomization is stratified by these variables. In addition, we will assess for confounding by a priori identified variables associated with distress and A1C including age, gender, race, primary language spoken at home, parental education, insurance status. If any of these analyses suggest confounding or are clearly imbalanced between groups, subsequent analyses will be adjusted accordingly.

Aim 1 primary outcome is A1C at 6 months. Because the amount of change depends strongly on the initial value at baseline we will control for baseline A1C as a covariate in the regression. We will treat A1C as a continuous outcome and apply linear regression model to estimate the mean between-arm difference and 95% confidence interval. The regression models will be specified as follows:

 $A1C \sim PRISM + baseline\ A1C + site + CGM + additional\ covariates$, where A1C is the outcome at 6 months, PRISM is the intervention indicator, baseline A1C, site, CGM status and other unbalanced confounders are the adjusted covariates. The coefficient of PRISM captures the adjusted mean differences in A1C between intervention and control arms, and will be tested using Wald t-test. In addition to the cross-sectional analysis of A1C at 6 months, we will also conduct repeated measures analysis using linear mixed effects models to examine the trajectories of A1C. This allows us a closer inspection of how participants respond to PRISM over time and examine

Protocol Version Number: 10

Protocol Version Date: 7/28/2021

whether the intervention benefits persist over time. The linear mixed regression models will be specified as follows: $A1C_{ij} \sim b_{0i} + PRISM_i + Time_j + PRISM_i \times Time_j + covariates$, where $A1C_{ij}$ is the A1C level for subject i at time j, b_{0i} is the subject specific random intercept to account for within-subject correlation due to repeated measures, and $PRISM_i \times Time_j$ is the group-by-time interaction term. When $Time_j$ is modelled as a discrete variable and baseline is the reference time point, the coefficients of the group-by-time interaction estimate the amount of differences in changes at later time points relative to baseline. Significance of these coefficients will be assessed using confidence intervals, and p-values from F-tests based on ANOVA and Kenward-Roger method. The property of the

For time-in-range (CGM data), we will use a 2 group comparison of the change from baseline in the percentage of sensor values in the target range (70-180 mg/dL) using a linear model adjusted for the baseline value and factors used to stratify randomization. All subjects with any CGM data will be included. Residual values will be examined for an approximate normal distribution. If values are highly skewed then transformation or non-parametric methods will be used instead.

Aim 2. Secondary outcomes include mean scores at 6-months for the PAID-T, CD-RISC, D-STAR, T1DAL, PHQ-8, BFSC, and SCI-R. We will model each outcome separately following a similar approach to the primary analysis for Aim 1.

Additional analyses and considerations. We will conduct a thorough process evaluation that includes: (a) intervention fidelity; and, (b) satisfaction queries. Multiple comparisons are a concern since we are collecting multiple measures from participants and are interested in several hypotheses. We minimize this problem by specifying a limited number of main hypotheses for each aim. The Benjamini-Hochberg procedure will be used to control the False Discovery Rate criterion at α =0.05 to correct for multiple testing in analyses that are not pre-specified. Likewise, in manuscripts and presentations, we will report the number of tests performed and interpret results within this context.

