Our research program is built on the premise that promoting resilience resources will reduce distress and improve outcomes. We have developed conceptual frameworks of resilience in pediatric illness, ^{20,22,23} affirmed associations between resilience resources and outcomes, ^{21,24-28} and developed and piloted a novel resilience resources intervention (Promoting Resilience in Stress Management, PRISM). ²⁹ PRISM is a skills-based, one-on-one training program consisting of two, 45-60 minute sessions followed by a family-meeting and supported by booster sessions and a digital app designed specifically for the adolescent population. Feasibility has been tested in adolescents with diabetes, ²⁹ cancer, ²⁹ cystic fibrosis, ³⁰ and currently in patients with craniofacial disorder and end-stage renal disease. We recently completed a pilot Randomized Controlled Trial (RCT) comparing PRISM to usual care among adolescents with cancer. Results suggest PRISM is feasible, highly acceptable, and associated with higher patient-reported resilience and quality of life, and lower risk of psychological distress 6 months following enrollment. ³¹ While initial findings for PRISM are promising in multiple groups, its efficacy among adolescents with T1D has not been tested.

Improving diabetes distress and health outcomes for adolescents with T1D requires innovative, developmentally-targeted, cost-feasible interventions designed to help patients effectively manage the stressors and challenges of T1D management in the context of everyday adolescent life. We propose a multi-site RCT comparing PRISM to usual care among youth with T1D (13-18 years with suboptimal glycemic control (elevated A1C) and diabetes distress as measured with a validated scale).

1.2. Hypotheses to be tested:

- 1. **Evaluate PRISM's efficacy in reducing A1C.** The primary outcome will be A1C at 6-months post-enrollment. *Hypothesis: PRISM will be associated with lower A1C compared to usual care at 6-months post-enrollment.* As an exploratory aim, for the subset of participants on continuous glucose monitors (approx. 30% of expected population), we will also examine PRISM's effect on sensor glucose time in range. A1C and time in range will be assessed for a total duration of 12 months post-intervention.

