5.1. Study design:⁸

This is a 4-year, multi-site RCT of PRISM compared to usual care among adolescents with T1D and clinically elevated distress scores (PAID-T≥30^{7,52}). We intend to enroll 250 adolescents and after ensuring they meet the rest of the eligibility criteria, expect to randomize 160-176 people. We will use a stratified randomization scheme with 1:1 allocation to PRISM or usual care (n=80-88 each). Randomization will be stratified by sitePRISM-assigned adolescents will be scheduled for two PRISM standard sessions (one-on-one skills-based sessions directed at stress-management, goal-setting, positive reframing, and meaning-making), followed by one "Coming Together" session (facilitated family-meeting during which the adolescent may share what was learned). All sessions will be offered in-person, by web-based video chat, or over the phone at a time interval of every 2 weeks. Boosters (1:1 check-in sessions with the interventionist probing about progress and roadblocks) will be delivered every 2 weeks until 3-months post enrollment, at which point they will be offered monthly until the end of month 6. The digital app (and/or paper worksheets) will be available throughout the intervention, but will not include individualized communication through the app. Surveys will be collected from adolescents in both arms upon

Protocol Version Number: 10
Protocol Version Date: 7/28/2021

enrollment and every 3 months for 12 months. Finally, A1C will be collected at each clinic visit and continuous glucose monitor (CGM) data (where applicable) will be collected.

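### Supportive A1C mixed model: a random intercept is the only visible correlation term, so if A1C correlation falls with time the 12-month interval is too narrow (minor, cheap to improve)

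*Combined protocol and SAP*

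**What the plan says.** Section 14.1 (Aim 1) makes the primary analysis a linear regression of 6-month A1C on arm, baseline A1C, site, CGM status and any further covariates. It then adds a mixed model for the A1C trajectory, with arm, time, arm-by-time and covariates. One of its purposes is to examine "whether the intervention benefits persist over time".

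The within-subject term "is the subject specific random intercept to account for within-subject correlation due to repeated measures". The visible text states no random slope, residual structure, unstructured covariance or robust variance. For the case in which visits are coded as separate categories compared with enrollment, the plan reads the interaction this way: "the coefficients of the group-by-time interaction estimate the amount of differences in changes at later time points relative to baseline". Its statement on inference is: "Significance of these coefficients will be assessed using confidence intervals, and p-values from F-tests based on ANOVA and Kenward-Roger method". The paragraph then breaks off in the available text.

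Three other statements bear on this:
- Section 14.1, analysis overview: "All analyses will be adjusted for site and baseline A1C".
- Section 5.1: "A1C will be collected at each clinic visit". The schedule in Section 5.3 backs A1C with a home kit at baseline, 6 and 12 months only; the 3- and 9-month values come from the chart if available.
- Section 1.2: "A1C and time in range will be assessed for a total duration of 12 months post-intervention".

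**The concern.** A random intercept alone implies one correlation for every pair of visits. The model then estimates a single within-subject variance, averaged over all pairs, and applies it to every change from baseline. If A1C correlation weakens with the gap between visits, that average is too small for the longest gap (0 to 12 months) and can be too large for a shorter one. Kenward-Roger corrects for small samples within the assumed covariance; it does not test or replace that covariance.

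The 12-month interaction is the contrast that speaks to persistence, and it spans the longest gap. An interval that is too narrow there would make a lasting effect look better established than the data show.

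The role of baseline A1C is also unsettled. In this model baseline is an outcome row, while the overview has every analysis adjust for it. The text does not say how both apply.

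**Working it through.** **The plan's own figures.** The documents give no operating figure for this model, only the nominal 5%. The detectable A1C difference in Section 10.4 belongs to the 6-month comparison and reproduces: 2.80 × 1.9 × √(2/50) = 1.06 by the normal approximation and 1.075 by the t-test, against a stated 1.1.

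**Inputs.** From the documents: A1C mean 9.1, SD 1.9; 80 or more randomized per arm; 20% attrition; kit-backed visits at 0, 6 and 12 months. Assumed, because the documents give no A1C correlation, at lags of 3/6/9/12 months:
- mild decay: 0.75/0.70/0.67/0.64
- moderate decay: 0.75/0.65/0.58/0.52
- autoregressive: 0.80/0.64/0.51/0.41

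**Closed form, complete visits.** The variance the model uses for a change from baseline is proportional to 2(1 − mean ρ), with the mean taken over all visit pairs. The true variance at visit j is proportional to 2(1 − ρ₀ⱼ). So R = model SE / true SE = √[(1 − mean ρ)/(1 − ρ₀ⱼ)], and type I error = 2[1 − Φ(1.96 R)].

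For visits 0/6/12, mean ρ = (2ρ₆ + ρ₁₂)/3:

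| Pattern | Mean ρ | R at 12 months | Type I, 12 months | Type I, 6 months |
|---|---|---|---|---|
| Constant | ρ | 1.00 | 5.0% | 5.0% |
| Mild | 0.680 | √(0.320/0.360) = 0.94 | 6.5% | 4.3% |
| Moderate | 0.607 | √(0.393/0.480) = 0.91 | 7.6% | 3.8% |
| Autoregressive | 0.563 | √(0.437/0.590) = 0.86 | 9.2% | 3.1% |

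If all five visits were complete, mean ρ would be 0.708/0.663/0.655 and the 12-month type I error about 8%, 10% and 13%. The schedule does not lead one to expect that, since 3- and 9-month values are chart-only.

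**Null simulation with Kenward-Roger.** 80 per arm, 80% observed at 6 and 12 months, missing completely at random, 4,000 replicates per cell (Monte Carlo error about ±0.7 points). Results are mild/moderate/autoregressive.

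| Test | A1C at 0/6/12 | Plus 3 and 9 months, 50% observed |
|---|---|---|
| 12-month coefficient | 6.9/6.9/8.1% (constant 5.0%) | 7.2/8.8/11.1% (constant 4.4%) |
| Joint interaction F-test | 5.3/5.0/4.9% | 5.0/4.5/4.9% |
| Arm-by-time slope, if time is linear | 7.0/6.9/8.1% (constant 5.1%) | 8.2/10.5/14.1% (constant 4.8%) |

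A separate simulation at 0/6/12 with 80% of follow-up observed gave 6.1/6.7/9.1% for the 12-month coefficient (constant 5.2%). At 62 per arm (62 × 0.8 ≈ 50 evaluable) it was 5.3/6.4/7.9%, with Monte Carlo error about ±1.0 point, so the mild cell there cannot be told from nominal.

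**Baseline in both roles.** Adding baseline A1C as a covariate while keeping it as an outcome row does not help: simulated 12-month type I error under decay was about 8-11%.

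**Precision.** A difference in change scores has variance proportional to 2(1 − ρ), and a baseline-adjusted contrast 1 − ρ². The SE ratio is √[2/(1 + ρ)]: 1.10 at ρ = 0.64, 1.15 at 0.52 and √(2/1.41) = 1.19 at 0.41.

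**The case against.** The strongest reply is that the documents give no A1C correlation, so they cannot show that any inflation exists; under constant correlation the planned test is correct. That stands, and every size here is conditional.

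Second, the p-values named in the plan are F-tests, and the joint F-test is near nominal in the discrete-time reading with incomplete visits. That also stands and narrows the point. It does not remove it, because the plan attaches confidence intervals to the individual coefficients. The discrete coding is itself stated conditionally; with linear time the interaction is one coefficient and its test is the exposed one.

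Third, the text after the Kenward-Roger sentence is lost or garbled. If it named another covariance, the point about correlation would fall.

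A reader might infer that the model is too liberal throughout, or that the trial's A1C conclusion is at risk. The documents support neither. With visits 0/6/12 the 6-month interaction is conservative, so precision is misallocated between visits. The only A1C hypothesis is at 6 months and is tested by a separate regression. No 12-month decision rule is set, so a false claim of persistence is a risk of interpretation and not a planned test that fails.

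Nor is it an error to use change from baseline: that contrast is unbiased and merely less precise.

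**Conclusion.** The point holds as a minor improvement to a supportive analysis. If A1C correlation declines with time, the 12-month interaction has a type I error of about 6-9% with A1C at 0/6/12 months, its SE being understated by roughly 6-14% (R of 0.94 to 0.86). The figure rises if 3- and 9-month chart values enter and is 5% if correlation is constant. The 6-month interaction errs the other way, at about 3-4%.

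This rests on the assumed correlations, on data missing completely at random in the simulations, and on the lost text naming no other covariance. The exposure is the single-visit coefficients and their intervals, chiefly at 12 months. The primary 6-month regression and the sample size are untouched.

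**What to change.** Replace the random intercept with an unstructured covariance across visits, fitted by REML with Kenward-Roger, and name heterogeneous Toeplitz as the fallback for non-convergence. Then settle the role of baseline in one way, not both:

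- **Preferred:** keep baseline A1C as an outcome row and drop the PRISM main effect, so that the arms are constrained equal at baseline. This keeps every participant with a baseline A1C, in line with the inclusion rule in Section 11.1.
- **Alternative:** model post-baseline A1C only, with baseline A1C by visit as a covariate. Participants with no follow-up A1C then contribute nothing.

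Either makes the 12-month contrast more precise than a difference in change scores. Simulated for the post-baseline version at 80 per arm, type I error under decay was 4.4-5.7%, and the 12-month SE under the planned model was 1.08-1.18 times as large. The preferred version was not simulated.

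State also whether the reported p-value is the joint F-test or the 12-month coefficient.

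Cost: SAP wording and more covariance parameters. An unstructured matrix for k visits has k(k + 1)/2, against 2 for the random intercept. For the post-baseline version that is a net 10 − 2 = 8 with four visits, or 3 − 2 = 1 with 6 and 12 months only. With baseline kept as a row it is 15 − 2 = 13, or 6 − 2 = 4. Non-convergence is a small risk: in the post-baseline simulations, 0 of 24,000 fits at 0/6/12, and with partial chart data 19 of 16,000 at 80 per arm and 22 of 8,000 at 62 per arm. A1C values must also be assigned to nominal visits, which a random intercept does not require; the window is for the sponsor to choose.

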14.2. Quality control procedures for collected data:33

For survey data, all participant surveys will be available by paper or online via the REDCap system, a secure HIPAA-compliant, high-quality data collection tool. The rationale for offering both paper-pencil and electronic versions is based on our prior experience where participants preferred the former,⁷⁸ which in turn facilitated more complete data collection. To ensure data quality, a RA will review for missing fields and call participants to clarify and query/complete individual missing items verbally. Data will be quality controlled by a double-checking mechanism (i.e., data double-entry via REDCap or double-entry/checking of manually entered data).

For medical record data, RA's will collect and upload CRF data at a frequency varying between 2 weeks and 6 months. To ensure reliability and validity of abstracted medical record data, we will use our current methods for training and quality control, including guided practice abstraction and independent abstraction with reconciliation by a trainer. A 10% random sample will be dual abstracted. A RA assignment will monitor and reconcile case report forms with RedCap data once monthly.

15. Confidentiality³⁴

15.1. Procedures to secure the data and/or biospecimens during storage, use, and transmission:

All medical record, health care utilization, survey data, and audio transcriptions will be coded and labeled with study identification numbers. All will be stored in original (hard copy) forms in locked cabinets (where relevant) and/or password-protected secure databases (for all electronic survey data). A1c data will be entered into the medical record (SCH) or sent to individual providers (BCM/TCH) and stored in compliance with each institutition's laboratory's protocols and procedures. At SCH, samples for HbA1c (DBS) are stored for 1-2 months at -20 C. The SCH lab keeps current and previous month samples, and samples are discarded at the first of the month. The storage locations are in the clinical lab in OC.10. Badge access is required to access this floor. At BCM/TCH, samples will be discarded seven days after receipt and processing. Storage location is WT.BB1.100 and badge access is required for this space. Original surveys will be saved for 10 years or until final analyses are completed, whichever occurs last, in order to ensure data quality. No identifiable patient information will be labeled on the surveys; all will be identified with a study-specific identifier with assigned identifier kept on a password protected encrypted server. Coded electronically saved study data will be banked indefinitely for future use by the group of investigators conducting the study and access will be controlled by the PI's. Pls will verify that additional analyses have IRB approval. Only study staff with human subjects training will have access, subject to approval by the PI. No data will be withdrawn from the study database. Results of initial analyses will be shared with participants if participants request on the consent form that they would like a summary of study results. When using web-based video chats for participant interaction, we will not store patient data/PHI within the web based applications.

Data will be stored in an electronic database (REDCap -Research Electronic Data Capture) using the participant's study identifier. REDCap data collection projects rely on

Protocol Version Number: 10
Protocol Version Date: 7/28/2021

a thorough study-specific data dictionary defined as an iterative self-documenting process by all members of the research team. We have conducted the iterative development and testing process previously, resulting in well-planned data collection. REDCap servers are housed in a data center and all web-based information transmission is encrypted. For the present study, we will use the REDCap system managed by the University of Washington Institute for Translational Health Sciences (ITHS). REDCap was developed specifically around HIPAA-Security guidelines and is recommended to researchers at various institutions by both Privacy Officers and Institutional Review Boards. REDCap has been disseminated for use locally and at other institutions and currently supports over 300 academic/non-profit consortium partners on six continents and over 20,000 research end-users (www.project-redcap.org). The REDCap data record may contain some identifying information. Subjects will be tracked using their study identifier. The identifiable data will be designated as "PHI" in the REDCap database which will allow us to exclude access to the identifiable information as necessary.

When Zoom is used, the following actions will be taken to protect confidentiality and privacy:

- 1. The latest version of Zoom that is available will be used.
- 2. The meeting room will be set to private.
- 3. A password/passcode will be required for meeting entry.

Note: The chat function will be utilized (as needed) for individual 1:1 communication between coach and participant, including sharing approved resources (e.g., PRISM cheatsheets), logistical information about PRISM (e.g., PRISM app code), and communicating if there are technical difficulties. Chat may also be considered for use for session content by patient request to accommodate specific needs (e.g., patient is unable to communicate verbally). No PHI would be communicated via chat at any time.

- **15.2.** Location where the data and/or biospecimens will be stored:
 - All will be stored in original (hard copy) forms in locked cabinets (at local sites) and/or password-protected secure databases (for all electronic survey data). A1c data will be stored in compliance with each institution's CLIA-certified laboratory policies and procedures.
- 15.3. Length of time data and/or biospecimens will be stored:10 years or until final analyses are completed, whichever occurs last.
- **15.4.** Individuals with access to data and/or biospecimens:

 Only members of the study-team will have access.
- **15.5.** Process for the transmission of data and/or biospecimens outside Seattle Children's:
 - **15.5.1.** List of data and/or biospecimens that will be transmitted:

Site RAs will maintain original copies of all consent forms and fax/email copies to the coordinating center for secure storage and tracking purposes. Upon study

Protocol Version Number: 10
Protocol Version Date: 7/28/2021

completion (last data collection for last patient), all materials will be coded (labeled only with study id) and faxed or scanned to the coordinating center for electronic storage.

15.5.2. Individual(s) who will transmit data:

Site RAs, study staff, and the principal investigator/site PIs

16. Provisions to Monitor Data to Ensure the Safety of Subjects³⁵

16.1. Plan to periodically evaluate the data collected regarding both harms and benefits to determine whether subjects remain safe:³⁶

This is a small multisite clinical trial of a supportive care intervention that presents no more than minimal risk. As such, data monitoring will be primarily carried out by the Lead RA and a small Data Safety Monitoring Committee (DSMC).

Safety monitoring will be the responsibility of a 3-member Data Safety and Monitoring Committee (DSMC) composed of professionals representing different disciplines and expertise (see table below). All members are independent of the protocol. The committee will be convened at the beginning of the study and then twice annually via conference calls, to provide input and guidance on the study evaluation and intervention protocols, including quality assurance and safety issues related to the protocols, as well as data handling activities. As above, in the event of an unanticipated patient death, the committee may convene an ad-hoc session and/or suspend the study to assess patient risk and/or necessary revisions to the protocol.

Data and Safety Monitoring Board

Member Name, Title	Discipline	Research Expertise				
[name] (Assistant	Pediatric Psychologist and	Pediatric Psychology, Health Behaviors				
Professor, Alpert Medical School,	Applied Statistician					
Brown University)						
[name] (Assistant	Adolescent Medicine	Pediatric Psychosocial and Health Services				
Professor, University of California Los						
Angeles)						
[name], OTR/L, CDE	Psychology and Behavioral	Diabetes Behavioral Research Interventions				
(Assistant Professor, USC)	Health					

16.2. Data reviewed to ensure safety of subjects:

DSMC members will provide input and feedback to the PI and Co-investigators, via e-mail and conference calls, related to (a) accrual rate, (b) study eligibility determination issues, (c) data completion rates including conformance with informed consent requirements, (d) intervention fidelity indicators, (e) adverse events, and (f) compliance with data management procedures. [name] (lead statistician) will oversee the summarization of online data to evaluate data completeness and protocol adherence. The Lead CRA will also send semi-annual reports summarizing recruitment and other site specific data (such as indicators of intervention delivery, occurrence of adverse events, and conformance with IRB requirements).

The committee will also receive information on questionnaire data, presented for the participants overall rather than by study group. This study will not have pre-set stopping rules, but the DSMB will have the option of requesting the data be unblinded and considering altering the study or

Protocol Version Number: 10
Protocol Version Date: 7/28/2021

stopping the study early. Although the full committee will meet twice-yearly, the PI or any member of the DSMB will be free to request to assemble the full committee at any time. Because committee members may be located at various sites, the committee meetings may be conducted by phone.

Data safety monitoring for the intervention will focus on assuring that subjects are not experiencing any significant or unexpected distress and that they are satisfied with the intervention components; we will monitor all complaints about the study. We do not anticipate stopping the study early for efficacy or harm, but the DSMB will have the option to consider such action in the event of a highly unexpected result. The DSMB will review the draft questionnaires to be sent to subjects and review any complaints that may be received from patients, family members, clinicians, or others. We do not anticipate any external factors such as findings from ongoing trials that will affect the safety of participants or the ethics of this research study.

16.3. Safety information collection procedures:

The DSMB, Lead RA and study team will regularly assess confidentiality of study participants. The following will be assessed and verified: All data will be maintained on secure computers in locked offices at Seattle Children's Research Institute (data collection center); the participant (and caregiver) has signed informed consent and HIPAA forms; all standard confidentiality/privacy rules and guidelines set by the Seattle Children's Research Institute are in compliance. A Certificate of Confidentiality will be obtained.

16.4. Frequency of cumulative data review:

The committee will be convened at the beginning of the study and then twice annually via conference calls, to provide input and guidance on the study evaluation and intervention protocols, including quality assurance and safety issues related to the protocols, as well as data handling activities.

16.5. Conditions that trigger an immediate suspension of the research:

Given the non-invasive nature of our proposed behavioral intervention and based on prior pilot studies,^{30,32} we expect minimal side effects and safety concerns as a result of the PRISM intervention. Thus, there are no pre-planned stopping rules for adverse events since these are not anticipated.

17. Use of Social Media

- **17.1.** Types of social media to be used and how:
- **17.2.** Measures in place to protect the privacy or confidentiality of subjects:³⁷
- **17.3.** Types of communications that will be submitted to the IRB for review:³⁸ n/a

Protocol Version Number: 10
Protocol Version Date: 7/28/2021

17.4. If user-generated content will be active, how it will be monitored and what actions will be taken to ensure subject safety and study integrity:

n/a

18. Research Related Injury³⁹

18.1. Available compensation in the event of research related injury: There is no compensation for research-related injury.

19. Recruitment Methods⁴⁰

19.1. When, where, and how potential subjects will be recruited:

Recruitment and retention will be promoted through a combination of clinic-based approaches and strategies we have successfully used previously.

Research staff at both sites will screen patients via review of clinic schedules and existing databases as well as via communication with clinicians, followed by a medical chart review to verify all eligibility except for diabetes distress to inform the in-clinic recruitment. At SCH, diabetes distress is typically screened at every in-person visit (standard of care) for all patients 13+ using the PAID-T. Clinic infrastructure provides instantaneous e-mail alerts to providers upon elevated scores. Our research team will be included in the e-mail notification of all patients with elevated scores (≥30 per published guidelines and mean clinic data).^{7,52} Research staff will screen these patients for other eligibility criteria and if eligible, will work with the provider team in clinic (as available) or contact the family by phone/video conference call (WebEx, Zoom, or Skype) to conduct a consent conference if the patient/family is interested.

Both sites may also use a mail approach to aid in in-clinic screening and recruitment. Upon reviewing clinic schedules and databases and screening patients for eligibility on criteria noted in the medical record or clinic databases (e.g., age, diagnosis, duration), patients will be mailed a letter in advance of their clinic visit or sent a letter via myChart in EPIC introducing them to the study and giving them the opportunity to "opt out" of future contacts if desired. If potentially eligible patients who receive the mailing do not opt-out of being approached about the study, we may call them to assess their interest and arrange to discuss the study by phone/video or meet them in-person at their upcoming clinic visit.

Both sites may post the approved flyer in clinic areas. The flyer may also be distributed to potential participants from clinical or research staff via myChart in EPIC or by e-mail if patients and families request more information.

At SCH, the screening visit will include verification of the PAID-T measure, and if all criteria are met, the full consent conference will take place (i.e., Phase 2 of Consenting; see Figure 2 below). At BCM and SCH, if a PAID-T is not available in the medical record, the screening visit will include verification of all criteria except for the PAID-T. If the patient is approached in clinic or by phone/video and expresses interest in participating in the study, the screening consent conference will take place (i.e., Phase 1 of Consenting; see Figure 2 in Consent/Assent Section below). If the patient is available in clinic, research staff will obtain written consent/assent for Phase 1/Screening prior to administering the PAID-T to the adolescent. If the patient is not in

Protocol Version Number: 10

Protocol Version Date: 7/28/2021

clinic and research staff is following up by phone/video, verbal consent/assent for Phase 1/Screening will be obtained via the information sheet prior to PAID-T administration. The patient will only be eligible for Phase 2 of Consenting and to be enrolled if the PAID-T is elevated (>=30). The same two-phase consenting process will occur at SCH if a PAID-T is unavailable at the time of consent (e.g., patient has opted out of taking standard of care measures in clinic, has not received the PAID-T as part of a tele-health visit or in-person visit or contacts the study team after receiving the recruitment letter but does not have a PAID-T in chart within the prior 12 months). In cases where the PAID-T is elevated upon screening and the patient/family subsequently decides not to participate, the provider will be notified (if not already notified).

